5.4.4 Pharmacodynamic Analyses

Analysis of biomarkers FGF 19, 21, and/or 23 is performed outside of this statistical analysis plan. Separate report will be prepared.

Summary statistics including mean, standard deviation, median, minimum and maximum for baseline, each post-baseline measurement, and change from baseline will be performed for glucose and phosphate levels for safety population.

5.4.5 Efficacy Analyses

Efficacy analysis will be performed based on both safety and evaluable populations.

Objective Response Rate and Disease Control Rate

The best overall tumor response (CR, PR, SD, PD and not evaluable), objective response rate and disease control rate will be tabulated by treatment group and overall on the safety population and evaluable population. The percent of subjects in each treatment group will be provided along with the 95% confidence interval of the percentage. In addition, the related listings will also be presented.

Percent change from the minimum sum of longest diameters (including baseline, if that is the minimum value, up to the preceding tumor assessment) and the percent change from baseline for the sum of longest diameters will be computed in the listings for target lesions. A waterfall plot will also be utilized to display the relationship between minimum sum of longest diameters change and current cancer types.

Progression Free Survival

Progression free survival will be estimated based on Kaplan-Meier estimate (product limit) for both safety and evaluable population. The median PFS and the 95% confidence interval will be estimated, and the corresponding Kaplan-Meier plots will be also presented.

5.4.6 Exposure Analyses

Dosing and Extent of Exposure

Duration of exposure is defined as the total number of days on the study drug. The following algorithm will be used to calculate the duration of study treatment exposure for subjects who took at least one dose of ARQ 087:

Duration of exposure (days) = [(date of last administration of study treatment) – (date of first administration of study treatment) + 1]

Temporary drug discontinuation will be ignored. If the date of the last administration is unknown, the date until which the dispensed drug should last without counting any extra drug provided will be used.

Treatment Compliance

A subject is considered compliant with the study protocol when study medication is administered at a compliance level of $\geq 80\%$. In order to evaluate safety of ARQ 087, replacement of non-compliant subjects will be allowed during the first 28 days of dosing.

Compliance will be calculated using the following equation:

$\% \text{ compliance} = (\text{Number of capsules actually ingested} / \text{number of capsules that should have been ingested per dose level}) \times 100$

This treatment compliance will be summarized for safety population per treatment groups and overall.

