**Table 4.1 Dosing Guidelines**

Cohort	Total Daily Dose a	Dose per Administration	Number of Subjects
Dose Escalation Cohorts: Part 1			
	25 mg	1 cap x 25 mg x twice a week	3-6 b
1 a	25 mg	1 cap x 25 mg x qod	3-6 b
2	25 mg	1 cap x 25 mg x qd	3-6 b
3	50 mg	2 caps x 25 mg x qd	3-6 b
4	100 mg	1 caps x 100 mg x qd	3-6 b
5*	150 mg	2 caps x 25 mg & 1cap x 100 mg x qd	3-6 b
6	200 mg	2 caps x 100 mg x qd	3-6 b
7	250 mg	2 caps x 25 mg & 2 caps x 100 mg x qd	3-6 b
8	325 mg	1 cap x 25 mg & 3 caps x 100 mg x qd	3-6 b
9	425 mg	1 cap x 25 mg & 4 caps x 100 mg x qd	3-6 b
10	550 mg	2 caps x 25 mg & 5 caps x 100 mg x qd	3-6 b
Food-effect a	400 mg	4 caps x 100 mg qd	at least 6
Expanded Cohort: Part 2			
Expanded e	300 mg	3 caps x 100 mg x qd under fasting conditions	approx. 50-60

\*Starting from Cohort 5, the dose escalation will follow a modified Fibonacci scheme (increase by 50%,

30%, and 25%)

To avoid potential non-compliance due to capsule burden, the dose escalation may be stopped at the dose level of 550 mg/daily

[figure not shown]
aTotal daily dose must be administered one hour prior to or two hours after the meal [Exceptions: 1) Cohort 1 is dosed every other day and 2) Food-effect Cohort]

bIf a DLT is seen in one of three treated subjects, an additional three subjects will be treated at the same dose level

cBased on the safety profile and PK results of the Food-effect cohort, the dose of 300 mg qd under fasting conditions has been defined as MTD/RP2D and should be further evaluated in the Expanded Cohort

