**Table 7.2 ARQ 087 Dose Reduction Schema**

Current Dose	Dose after Reduction
Dose Level 1: 3 capsules qd (300 mg daily)	Dose Level 2: 2 capsules qd (200 mg daily)
Dose Level 2: 2 capsules qd (200 mg daily)	Dose Level 3: 1 capsule qd (100 mg daily)
Dose Level 3: 1 capsule qd (100 mg daily)	

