## 7.4 Treatment Compliance

A subject is considered compliant with the study protocol when study medication is administered at a compliance level of  $\geq 80\%$ . In order to evaluate the safety of ARQ 087, replacement of non-compliant subjects will be allowed during Cycle 1 of Treatment Period 2/Continuous Dosing.

Compliance will be calculated using the following equation:

(Number of capsules actually ingested / number of capsules that should have been ingested per dose level) x 100 = % compliance

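### Compliance counts 25 mg and 100 mg capsules equally over an undefined denominator, and no planned summary shows how much of the planned dose was delivered

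*SAP*

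**What the plan says.** Protocol 7.4 gives the compliance formula as "Number of capsules actually ingested / number of capsules that should have been ingested per dose level) x 100 = % compliance". SAP 5.4.6 repeats it as "Number of capsules actually ingested} / \text{number of capsules that should have been ingested per dose level" (stray characters are formula typesetting), and both set the threshold at 80% or more: "A subject is considered compliant with the study protocol when study medication is administered at a compliance level of" that value. The one stated use of the threshold is that non-compliant subjects may be replaced early, in Cycle 1 of continuous dosing (protocol) or the first 28 days (SAP). None of the populations in SAP section 4 uses it.

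The drug comes as 25 mg and 100 mg capsules (protocol 7.1). Several Part 1 cohorts mix the two. Cohort 9, for example, takes "1 cap x 25 mg & 4 caps x 100 mg x qd" (protocol Table 4.1). The Expanded Cohort uses one strength only, and its reduction steps begin at "Dose Level 1: 3 capsules qd (300 mg daily") and go to two capsules and then one (protocol Table 7.2). Outside that schema, protocol 7.3 sends a reduced subject to the previous cohort's dose. Table 7.1 allows restart after holds of up to 21 days.

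SAP 5.4.6 defines duration of exposure as last dose date minus first dose date plus 1, and adds: "Temporary drug discontinuation will be ignored". Protocol 10.3.2 also disregards temporary discontinuation. The SAP's exposure section plans no cumulative dose, count of days dosed, or dose intensity.

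**The concern.** There are three linked weaknesses. First, a count that gives a 25 mg and a 100 mg capsule the same weight does not track dose in a mixed-strength cohort, so an 80% cut on the count is not an 80% cut on the dose. Second, the denominator, "number of capsules that should have been ingested per dose level", leaves open which dose level is meant after a reduction and what happens to held days. Two programmers could give the same subject different compliance values. Third, duration includes held days, and compliance on some readings stays at 100% after a reduction. The two exposure measures together therefore need not reveal that a subject received much less than planned.

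The stake is interpretation. Safety and tolerability is the primary objective, and further evaluation of the recommended Phase 2 dose is a secondary one. Whether 300 mg daily can be sustained is a direct tolerability question, and no planned table answers it in terms of dose delivered. In Part 1 the 80% rule can also affect who is replaced in cohorts of 3-6 subjects.

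**Working it through.** The plan states no figure on this point to reproduce. As a check on inputs, the total daily doses in SAP Table 1 were rebuilt from their capsule make-up, and they match.

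**1. Capsule count against mg at a fixed dose.** Count % = capsules taken / capsules due. mg % = mg taken / mg due. One capsule omitted every day:

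| Cohort | Daily capsules | Omitted | Count % | mg % |
|---|---|---|---|---|
| 5 | 2×25 + 1×100 = 150 mg | one 25 mg | 2/3 = 66.7 | 125/150 = 83.3 |
| 7 | 2×25 + 2×100 = 250 mg | one 25 mg | 3/4 = 75 | 225/250 = 90 |
| 8 | 1×25 + 3×100 = 325 mg | one 25 mg | 3/4 = 75 | 300/325 = 92.3 |
| 9 | 1×25 + 4×100 = 425 mg | one 100 mg | 4/5 = 80 | 325/425 = 76.5 |

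Enumerating every intake pattern over 28 days gives the extremes on each side of the cut:

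| Cohort | Lowest mg % with count ≥80% | Highest mg % with count <80% |
|---|---|---|
| 5 | 61.9 (count 81.0) | 89.9 (count 79.8) |
| 7 | 68.6 (count 80.4) | 91.8 (count 79.5) |
| 8 | 75.8 (count 80.4) | 93.7 (count 79.5) |
| 9 | 76.5 (count 80.0) | 93.3 (count 79.3) |

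If whole daily doses are missed, the two measures agree in every cohort: 23/28 = 82.1% and 22/28 = 78.6%. In Cohorts 1-4 and 6, the Food-effect Cohort and the Expanded Cohort they agree for any pattern at a fixed dose. Protocol Cohort 10 also mixes strengths but is not in SAP Table 1.

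**2. After a one-step reduction, with full adherence at the lower dose.** Against the current level, the count is 100% in every case. Against the assigned level it is:

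| Reduction (mg) | Capsules | Count % | mg % of assigned |
|---|---|---|---|
| 100 to 50 | 1 to 2 | 200 | 50 |
| 150 to 100 | 3 to 1 | 33.3 | 66.7 |
| 200 to 150 | 2 to 3 | 150 | 75 |
| 250 to 200 | 4 to 2 | 50 | 80 |
| 325 to 250 | 4 to 4 | 100 | 76.9 |
| 425 to 325 | 5 to 4 | 80 | 76.5 |
| Expanded, 300 to 200 | 3 to 2 | 66.7 | 66.7 |

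**3. Dose delivered in the Expanded Cohort.** Relative dose intensity = total mg taken / (300 mg × exposure days). The timings are assumptions, within the permitted holds and reduction steps.

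- 8 weeks at 300 mg, 2-week hold, 6 weeks at 200 mg: exposure 112 days; (56×300 + 42×200) / (112×300) = 25,200/33,600 = 75%.
- 4 weeks at 300, 3-week hold, 4 weeks at 200, 2-week hold, 11 weeks at 100: exposure 168 days; (28×300 + 28×200 + 77×100) / (168×300) = 21,700/50,400 = 43.1%.
- 14 days at 300, 21-day hold, 21 days at 200: exposure 56 days, 35 of them dosed; 8,400/16,800 = 50%.
- A grid with one hold and one reduction (spans of 56, 84 and 168 days; holds of 7, 14 and 21 days; 14 or 28 days before the hold): 50% to 75%.

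**4. Compliance for the 56-day subject under each reading.** Capsules taken: 14×3 + 21×2 = 84.

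- Current level, hold excluded: 84/84 = 100%.
- Current level, hold included: 84/126 = 66.7% with held days at 200 mg, or 84/147 = 57.1% with held days at 300 mg.
- Assigned level, hold excluded: 84/105 = 80%.
- Assigned level, hold included: 84/168 = 50%.

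The subject's class at the 80% cut therefore depends on a rule that neither document states.

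**The case against.** The strongest reply is that the practical reach is small. The mixed-strength cohorts in SAP Table 1 hold 12-24 subjects (four cohorts of 3-6). Error at a fixed dose needs partial-day intake skewed to one strength, while exclusion criterion 5 bars subjects unable or unwilling to swallow the complete daily dose. The threshold triggers only optional early replacement. The analyses are descriptive, and 300 mg was chosen on the safety profile and Food-effect PK data. All of this stands and limits the severity.

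A reader might infer that the denominator resets to the current dose. The text does not say so. Table 7.2 labels its reduction steps as dose levels, which makes that reading plausible for Part 2, but the supportable fault is that the term is undefined.

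A reader might also infer that the delivered dose is concealed. It is not. Dose changes must be captured in the EDC (protocol 7.3), eCRF data are to be listed as appropriate (SAP 5.2), and TEAEs leading to interruption, or to interruption then reduction, are tabulated (SAP 5.4.7). These tables count subjects with events, however, not dose lost. They have no row for a reduction without a preceding interruption or for a hold not caused by an adverse event, and a listing is not a summary.

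It is also fair to say that adherence to a prescribed reduced dose is a different quantity from dose intensity. A subject who takes a reduced dose in full is properly 100% adherent. That supports reporting both measures.

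**Conclusion.** The point holds as a minor to moderate weakness. In Cohorts 5, 7, 8 and 9 the 80% rule can misclassify a subject who takes part of a day's capsules, in either direction. The documents do not support saying that it does misclassify subjects, or that it can do so in this way in the Expanded Cohort, where count and mg agree at a fixed dose.

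The undefined denominator affects every cohort in which doses are reduced or held. Against the assigned level the count is erratic where capsule numbers and strengths change (33% to 200% after one step). Against the current level, with holds left out, it is 100% for a fully adherent subject whatever dose was lost.

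The more consequential gap is that delivered dose is not summarised, above all for the approximately 50-60 subjects planned at 300 mg. The illustrations of about 43% to 75% rest on assumed hold and reduction timings. They show what the planned summaries could miss and do not predict what will occur. The 43% case is demanding: two reductions, a hold at the 21-day limit and a 24-week course.

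**What to change.** In protocol 7.4 and SAP 5.4.6:

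- Compute compliance as mg ingested / mg prescribed × 100, and apply the 80% cut to that ratio.
- State that the denominator follows the prescribed dose, including after a reduction, and state how held days count.
- Keep the existing duration of exposure. Add days dosed, excluding interruptions.
- Add relative dose intensity = total mg ingested / planned mg at the starting dose and schedule over the exposure period × 100. Held days and reductions stay in the denominator at the starting dose, and the every-other-day cohort uses its scheduled dosing days.
- Summarise the new measures for the Expanded Cohort and by Part 1 dose level.

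No visit, dose or clinical rule changes. The cost is revised wording, one extra table and a less favourable exposure figure. Dose changes are already in the EDC, and accountability logs hold dose and quantities dispensed and returned (protocol 7.1.1). The documents do not show that capsules taken by strength are in the analysis database, so that must be confirmed first.

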5.4.7 Analyses of Safety Variables

All analyses for the safety variables will be performed on safety population. Safety variables include adverse events, laboratory parameters, vital signs, ECOG performance status, 12-lead ECG and physical exams.

Descriptive statistics will be calculated for quantitative safety data, frequency counts and percentages will be compiled for classification of qualitative safety data. All percentages will be calculated based on the number of subjects in the safety population, unless otherwise indicated. Baseline is defined as the last non-missing value prior to the first dose date or on day 1, unless otherwise noted.

Adverse Events

Adverse events will be evaluated for severity using NCI-CTCAE, version 4.03. AE summaries will include treatment-emergent adverse events (TEAEs).

A TEAE is defined as:

- an AE which is not present prior to the first dose of ARQ 087 and started after taking the study drug during the treatment period or within 30 days after the last dose of the study drug;
- an AE which is present prior to the first dose of ARQ 087 and increased in severity after taking study drug during the treatment period or within 30 days after the last dose of study drug;
- an AE which is considered study drug-related regardless of the start date of the event.

All TEAEs will be coded using Medical Dictionary for Regulatory Activities (MedDRA[®]) Version 15.1 and summaries will be presented by system organ class and preferred term. Separate TEAE summaries will be generated for the following categories:

- All TEAEs
- Severe TEAEs (Grade 3 or higher)
- SAEs
- TEAEs related to study drug
- TEAEs leading to treatment discontinuation
- TEAEs leading to treatment interruption
- TEAEs leading to treatment interruption then dose reduction
- TEAEs resulting in death
- TEAEs listed according to maximum severity
- TEAEs classified as DLTs

TEAEs will be summarized by presenting the number and percentage of subjects having at least one TEAE in each system organ class and preferred term. A subject with multiple occurrences of the same TEAE will be counted only once in the AE category.

Separate TEAE summaries will be presented by system organ class, preferred term, and maximum CTCAE 4.03 grade. A subject with multiple CTCAE grades for the same TEAE will be summarized under the maximum CTCAE grade recorded for the event.

Laboratory Test

Summary statistics for baseline, each post-baseline measurement, and change from baseline for each post-baseline measurement will be presented for all parameters in the safety population.

Toxicities will be graded according to the NCI CTCAE, Version 4.03. Shift table of toxicity grade for NCI CTCAE specified laboratory tests will also be presented in the safety population per treatment groups and overall.

Baseline is defined as the last non-missing value assessment made prior to the first dose of study medication, which is, for most subjects, the clinical laboratory assessment taken on Day 1 prior to the first dose. If it's missing, the laboratory assessment at screening (including pre-study visit and unscheduled visit) will be used as baseline value.

If lab results contain symbols like "<", ">", "≥" or "≤", extract the numeric value as the limit, Example: if result is ">0.1", "0.1" will be used for analysis.

Vital Signs

Summary statistics for baseline, each post-baseline measurement, and change from baseline for each post-baseline measurement will be presented for each vital sign parameter.

Individual absolute vital sign values and the change from baseline will be summarized descriptively for each treatment group and overall, by schedule of assessments.

ECOG Performance Status

Number and percentage of subjects having each ECOG performance status level will be presented for baseline and each post-baseline measurement, per treatment groups and overall.

In addition, the shift table comparing post baseline to baseline will also be presented per treatment groups and overall.

12-lead ECG

12-lead ECG absolute individual parameters [PR interval, QRS interval, QT interval, QTcF interval, QTcB interval and Summary (Mean) Ventricular Rate] and the change from baseline will be summarized per treatment groups and overall per assessment. All ECG measurements will be presented in the data listings.

Physical Examination

Data from physical examinations will be presented in the data listings as per subject per visit per body system, using safety population.

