#### **4.6 Study Duration**

Subjects will receive treatment with ARQ 087 until progression of disease (clinical or radiological), unacceptable toxicity, or another of the discontinuation criterion is met (see Section 5.8). It is expected that most subjects will receive between one and six cycles of ARQ 087 for a treatment period of four to 24 weeks.

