4.2 Safety Population

Subjects who received any amount of ARQ 087 are included in the safety population.

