11 MOCK-UP TABLES AND LISTINGS OF APPENDICES

Raw measurements will be reported to the number of significant digits as captured electronically or on the CRF. The mean and median will be displayed to one decimal place beyond the number of decimal places the original parameter is presented, and the measure of variability (e.g., standard deviation) will be displayed to two decimal places beyond the number of decimal places the original parameter is presented. Minimums and maximums will be reported to the same number of significant digits as the parameter. Calculated percentages will be reported with 1 decimal place. When count data are presented as category frequencies and corresponding percentages, the percent will be suppressed when the count is zero. If there are missing observations for the variable, percentages will not be displayed for this row. Listings of subjects will be sorted by subsequent by subject ID. When available, listings will also be sorted by study day.

LIST OF FIGURE

LIST OF TABLES

LIST OF LISTINGS

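### By-visit ECOG percentages default to the whole safety population as denominator, so they mix attrition with performance status

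*SAP*

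**What the plan says.** SAP 5.4.7 gives one general rule for safety tables: "All percentages will be calculated based on the number of subjects in the safety population, unless otherwise indicated". SAP 4.2 fixes that population: "Subjects who received any amount of ARQ 087 are included in the safety population". It does not change from visit to visit.

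The ECOG paragraph of SAP 5.4.7 then asks for a table by visit: "Number and percentage of subjects having each ECOG performance status level will be presented for baseline and each post-baseline measurement, per treatment groups and overall". It names no denominator, so the exception clause in the general rule is not used and the default applies. The next sentence adds an ECOG shift table: "In addition, the shift table comparing post baseline to baseline will also be presented per treatment groups and overall". That sentence mentions neither percentages nor visits.

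Protocol 4.6 sets the expected time on treatment: "It is expected that most subjects will receive between one and six cycles of ARQ 087 for a treatment period of four to 24 weeks". The note to Protocol 5.5.2 lets subjects without Grade 3/4 toxicity after four cycles at one dose level move to four-weekly evaluation, by agreement. ECOG is otherwise scheduled on Day 15 of Cycle 2 and later (Protocol Appendix 1; SAP Table 4).

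**The concern.** A fixed denominator suits a cumulative question, such as how many treated subjects ever had a given adverse event. It does not suit a cross-sectional one, such as how performance status is distributed at Cycle 4. Subjects with no value at the visit stay in the denominator but can appear at no ECOG level, so they pull every level down.

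Missing values at later visits are expected in this design. Many subjects will have stopped by then, and some who remain may skip Day 15 visits by agreement. The second group is selected for good tolerability.

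Safety and tolerability are the primary objective (SAP 2.1.1) and are reported descriptively. A reader following one ECOG row across visits could mistake loss of subjects for stable or better performance status.

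**Working it through.** **Plan's own figure.** Neither document states an ECOG percentage or a retention rate, so there is nothing to reproduce.

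**Inputs from the documents.** Default denominator (SAP 5.4.7); safety population (SAP 4.2); Expanded Cohort of about 50-60 subjects, reported as its own group (SAP 2.2.1 and 5.2); ECOG 0-2 at entry (Protocol 3.1).

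**Assumed inputs.** All counts of subjects assessed and of subjects at each ECOG level.

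**Formula.** Let N be the safety population of the group, n the number assessed at the visit and x the number of those at a given level.

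- Printed under the default: x/N
- Among those assessed: x/n
- Hence printed = (x/n) × (n/N)

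The printed percentage falls from baseline whenever the share among those assessed grows by a factor smaller than N/n.

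**Example 1, N = 55 (midpoint of 50-60).**

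- Baseline, all assessed, 10 at ECOG 2: 10/55 = 18.2%. ECOG 0-1: 45/55 = 81.8%.
- Later visit, 20 assessed, 8 at ECOG 2: among those assessed 8/20 = 40.0%; printed 8/55 = 14.5%.
- Check: the share grew by 40.0/18.2 = 2.2, less than 55/20 = 2.75, so the printed figure falls.
- ECOG 0-1 is then at most 12/55 = 21.8%, and the levels sum to 20/55 = 36.4%.

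Keeping 40% of those assessed at ECOG 2 and changing only the number assessed:

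| Assessed | At ECOG 2 | Among assessed | Printed | Against 18.2% at baseline |
|---|---|---|---|---|
| 30 | 12 | 40.0% | 12/55 = 21.8% | rises |
| 25 | 10 | 40.0% | 10/55 = 18.2% | flat |
| 20 | 8 | 40.0% | 8/55 = 14.5% | falls |

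**Example 2, N = 60, worsening among those who stay.**

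| Assessed | At ECOG ≥2 | Printed (x/60) | Among assessed (x/n) |
|---|---|---|---|
| 60 | 6 | 10.0% | 10.0% |
| 45 | 9 | 15.0% | 20.0% |
| 30 | 9 | 15.0% | 30.0% |
| 15 | 6 | 10.0% | 40.0% |

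The share among those assessed quadruples, while the printed figure ends where it began. The printed levels sum to 100%, 75%, 50% and 25%.

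**Example 3, N = 60, worsened subjects leave first.**

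| Assessed | At ECOG ≥2 | Printed (x/60) | Among assessed (x/n) |
|---|---|---|---|
| 60 | 6 | 10.0% | 10.0% |
| 45 | 4 | 6.7% | 8.9% |
| 30 | 2 | 3.3% | 6.7% |
| 15 | 1 | 1.7% | 6.7% |

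Both columns fall. The fixed denominator falls further, but changing the denominator does not by itself reveal the decline.

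**The case against.** The strongest reply is that the rule is only a default, and that table shells often state their own denominators. SAP 11 refers to mock-ups, but the text available for review has only the list headings. The finding therefore rests on the SAP's narrative text; a shell that names the denominator would settle it. This reservation stands.

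A second reply is that the loss of subjects is not concealed. Counts are printed beside percentages, the levels visibly fail to sum to 100%, an ECOG shift table is planned, and ECOG is assessed at the End of Treatment visit (Protocol 5.6). A reader might infer that the SAP hides deterioration; for these reasons the documents do not support that. In Example 1, ECOG 0-1 drops from 81.8% to at most 21.8%, which nobody reading the whole column would take for improvement. What remains is that a single row can mislead.

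A third reply is that an observed-case denominator has its own bias. Example 3 confirms this, so a second summary is needed.

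Two further inferences go too far. A reader might take the SAP 11 rule, "If there are missing observations for the variable, percentages will not be displayed for this row", as contradicting 5.4.7. It governs display only and is compatible with either denominator. A reader might also extend the by-visit problem to the ECOG and laboratory shift tables. The SAP does not say that those tables carry percentages or are made by visit. If they use a worst or last value, subjects who leave still contribute.

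**Conclusion.** The point holds for the by-visit ECOG table. As written, SAP 5.4.7 scales every level's percentage by the fraction still assessed, so a rising share of poor performance status among assessed subjects can print as flat or falling. The size depends on retention, which the documents do not give. If 40% of those assessed are at ECOG 2 or worse, the table prints 20.0% when half the group is assessed and 10.0% when a quarter is. The direction over time also depends on retention: in Example 1 the printed figure rises, stays flat or falls as 30, 25 or 20 of 55 are assessed.

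The consequence is limited. The table is descriptive, SAP 5.1 plans no hypothesis tests, and no dose, stopping or enrolment rule uses an ECOG percentage. The default denominator is the right one for TEAE incidence.

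**What to change.** In SAP 5.4.7:

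1. State that percentages in the by-visit ECOG table use safety-population subjects with a non-missing value at that visit, and show n assessed and n missing for each visit and group.
2. State that any percentages in shift tables use subjects with both a baseline and a post-baseline value.
3. Add a summary of worst post-baseline ECOG in the safety population, including the End of Treatment assessment, with the number of subjects who have no post-baseline value.
4. Keep the full safety population as denominator for TEAE incidence.

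SAP 11 needs no change on this account. The cost is a few sentences in the SAP, a denominator change in programming and one extra table. All the data are already collected, and no protocol amendment is needed.

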## 7.3 Dose Modifications

In general, once the dose of ARQ 087 has been modified for a subject, all subsequent cycles should be administered to that subject at the modified dose. The modified dose will be considered the maximum dose for all subsequent cycles for that subject.

When a drug-related toxicity is observed, dose delays and/or reductions in ARQ 087 administration are allowed. If dose reduction is indicated, a subject should be assigned to the previous (lower) cohort dose (dose re-escalation is not permitted). In the event of a dose modification, the dose change(s) must be captured in the electronic data capture (EDC) system. If questions or considerations regarding dose modification arise or a specific dose modification is needed, ArQule's Medical Monitor or designee should be consulted.

If the subject experienced a DLT, such subject should be permanently discontinued from the treatment. During the dose escalation period, intra-subject dose escalation is not allowed. Once the MTD/RP2D is reached, intra-subject dose escalation may be considered to optimize the dose level taking into consideration the available dosage strengths. A maximum of one intra-subject dose escalation per subject may be considered.

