**Table 7.1 Dose Delays/Reductions for Drug-Related Toxicity**

Event Grade	Action
Grade 1 or 2, including significant increase in LFTs (as assessed by the Investigator) and alopecia	Continue current dose level, unless dose interruption/modification may be clinically indicated, e.g., due to significant increase in LFTs
Grade 3-4 nausea, vomiting or diarrhea lasting < 24 hours	Withhold ARQ 087 until recovery to Grade 1 or baseline. If recovery occurs within 24 hours, restart ARQ 087 at the current dose level.
Grade 3-4 toxicity, including nausea, vomiting or diarrhea lasting $\geq$ 24 hours	
Withhold ARQ 087 until recovery to Grade 1 or baseline.
 
 
- If recovery occurs within 14 days, restart ARQ 087 at the dose and schedule of the previous cohort for all subsequent cycles, unless further dose reduction is required.
 
- If recovery occurs within 21 days of the drug hold, ARQ 087 may be restarted upon agreement between the Investigator and the Sponsor's Medical Monitor. Treatment should be restarted at the dose and schedule of the previous cohort for all subsequent cycles, unless further dose reduction is required.
 
- If recovery occurs after more than 21 days of the drug hold, ARQ 087 should be permanently discontinued
 

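### The SAP has no summary of all TEAEs leading to dose reduction, so reductions made without a prior hold are not identified and their frequency at 300 mg qd could be understated

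*SAP*

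**What the plan says.** Three of the ten TEAE summaries in SAP 5.4.7 sort events by a change to treatment: those leading to discontinuation, "TEAEs leading to treatment interruption" and "TEAEs leading to treatment interruption then dose reduction". The others cover all TEAEs, Grade 3 or higher, serious, drug-related, fatal, by maximum severity, and DLTs. The general rule is broad: "TEAEs will be summarized by presenting the number and percentage of subjects having at least one TEAE in each system organ class and preferred term".

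On dosing, Protocol 7.3 says: "When a drug-related toxicity is observed, dose delays and/or reductions in ARQ 087 administration are allowed". Table 7.1 then splits by grade:

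- **Grade 1 or 2:** "Continue current dose level, unless dose interruption/modification may be clinically indicated". No hold is required before a modification.
- **Grade 3-4** (other than nausea, vomiting or diarrhea lasting under 24 hours, which restarts at the current dose): first "Withhold ARQ 087 until recovery to Grade 1 or baseline", then, on timely recovery, "restart ARQ 087 at the dose and schedule of the previous cohort for all subsequent cycles".

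SAP 5.4.6 covers duration of exposure and capsule compliance. It plans neither a count of subjects reduced nor a dose intensity. Protocol 7.3 requires dose changes to be captured in the EDC system, and SAP 5.2 plans listings of eCRF data as appropriate.

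**The concern.** The SAP category is narrower than the protocol rule it reports on. The protocol allows a delay, a reduction, or both. The SAP tabulates the delay, and the delay followed by a reduction, but not the reduction alone.

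Safety and tolerability is the primary objective, and further evaluation of the RP2D is a secondary one. Protocol 7.3 does not permit re-escalation after a reduction, so a subject reduced for toxicity does not return to 300 mg. DLTs are counted over the first 28 days, while Protocol 4.1.1 puts steady state at about 35 days. Tolerability after that window has to be read largely from adverse events, discontinuations, holds and reductions. Persistent lower-grade toxicity managed by a reduction alone is the part with no row of its own.

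**Working it through.** The plan states no dose-reduction figure, so there is nothing to reproduce. The check has two steps: trace each route in the protocol to the SAP summaries, then bound the size of the gap.

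**Step 1. Routes to a lower dose, against the SAP 5.4.7 summaries by action taken**

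| Route | Source | Identified as dose-reducing? |
|---|---|---|
| Grade 3-4: hold, then restart lower | Table 7.1 | Yes, in "TEAEs leading to treatment interruption then dose reduction" |
| Grade 1-2: hold, then lower dose | Table 7.1, Protocol 7.3 | Yes, same summary |
| Grade 1-2: lower dose, no hold | Table 7.1, Protocol 7.3 | No |

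The third route meets neither interruption category, and it is not a discontinuation.

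**Step 2. Does another planned analysis recover the count?** Duration of exposure is last dose date minus first dose date plus 1, whatever the dose. Compliance divides capsules taken by capsules due at the dose level, so a subject who takes every capsule at a reduced level can score 100%. Neither shows a reduction. Listings would show it case by case but give no rate.

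**Step 3. Size**

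Inputs:
- N = 50 to 60 in the Expanded Cohort (SAP 2.2.1).
- R = true share of subjects with a toxicity-driven reduction. Not in the documents; assumed 10% to 40%.
- s = share of those reductions made without a hold. Not in the documents; assumed 0 to 50%.

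Formulas: tabulated rate = R × (1 − s); shortfall = R × s.

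| R | s = 0 | s = 10% | s = 25% | s = 50% |
|---|---|---|---|---|
| 10% | 10.0 (0) | 9.0 (1.0) | 7.5 (2.5) | 5.0 (5.0) |
| 20% | 20.0 (0) | 18.0 (2.0) | 15.0 (5.0) | 10.0 (10.0) |
| 30% | 30.0 (0) | 27.0 (3.0) | 22.5 (7.5) | 15.0 (15.0) |
| 40% | 40.0 (0) | 36.0 (4.0) | 30.0 (10.0) | 20.0 (20.0) |

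Entries are the tabulated rate in percent, with the shortfall in percentage points in brackets. One omitted subject is 100/50 = 2.0 points at N = 50 and 100/60 = 1.7 points at N = 60.

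The chance that at least one subject is affected, treating subjects as independent, is 1 − (1 − R × s)^N. For R = 20% and s = 10% this is 1 − 0.98^50 = 0.64 at N = 50 and 1 − 0.98^60 = 0.70 at N = 60. If s = 0 it is 0.

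**The case against.** The strongest reply has four parts.

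1. **The events are not lost.** A reader might infer that a directly reduced event falls in no table. The documents do not support that. It appears among all TEAEs and in the maximum-severity table, in the drug-related, Grade 3 or higher and serious tables where it qualifies, and in the listings. Only the label for the action taken is missing. This stands.

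2. **The category is not wrong for what it names.** The SAP does not call it an overall dose-reduction rate. It becomes an undercount only if it is read as one and direct reductions occur. This stands, but it is the only reduction summary listed, so it is the figure a reader would reach for.

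3. **Table 7.1 narrows the gap.** Grade 3-4 reductions go through a hold and fit the SAP category. For Grade 1-2 events the default is to continue the current dose. This stands: the gap is mainly Grade 1-2 events and may be small.

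4. **The SAP already goes beyond the protocol, and not all of it can be seen.** Protocol 10.3.3.1 lists no interruption or reduction summary. The list of tables in SAP 11 shows no entries in the text available, so a dose-modification table there cannot be ruled out. This limits the claim to the summaries named in SAP 5.4.7 and the analyses in 5.4.6.

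None of this supplies a count of subjects reduced without a hold.

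**Conclusion.** The gap in the listed summaries is clear from the text; its size is unknown. Reductions without a prior hold are allowed by the protocol but are not identified as dose-reducing in any summary listed in SAP 5.4.7, and SAP 5.4.6 does not recover them.

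It would go too far to say that the reduction rate at 300 mg qd is understated. The documents give neither the reduction rate nor the share made without a hold. What they support is that it could be understated, by the product of the two. That is zero if every reduction follows a hold, and 0 to 20 points over the assumed ranges, where 20 is the extreme corner (R = 40%, s = 50%). For a reader who takes the summary as the overall reduction rate, the error can only be downward. No hypothesis test or stated decision rule depends on this table, so the case for the change is completeness on the primary tolerability objective at almost no cost.

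**What to change.** In SAP 5.4.7, replace the conditional category with *TEAEs leading to dose reduction (with or without prior interruption)*. Keep TEAEs leading to treatment interruption as its own category. If the present split is of interest, keep interruption followed by reduction as a sub-row. A count of subjects with any dose reduction, by treatment group, would be a useful optional addition to SAP 5.4.6.

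The cost is about one line of SAP text and the matching table shell. Dose changes must already be captured in EDC. The one point to confirm is that the adverse event or dosing record links a direct reduction to the event that caused it, since the documents do not show the eCRF action-taken options. No dosing rule changes.
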